#### **9.5.2.4. Vital Signs**

Descriptive statistics will be provided for the vital sign measurements by scheduled time of evaluation and by treatment group, as well as for the change from baseline. The baseline value is defined as the last non-missing value before the initial administration of study treatment. A listing of vital sign data will be generated.

### 9.5.2.5. Other

Listings of all other safety endpoints (e.g., physical examination findings) will be generated.

### 9.5.3. Pharmacokinetics Analysis

Pharmacokinetic analysis and statistical analysis of PK endpoints will be conducted in accordance with the protocol, SAP, and the Daiichi Sankyo Non-Compartmental Analysis Guidelines.

#### 9.5.3.1. Pharmacokinetic Parameters

Pharmacokinetic and statistical analysis will be performed using appropriate software; e.g., Phoenix™ WinNonlin® (Version 8.1 or higher, Certara, L.P.) and/or SAS® (Version 9.4 or higher, SAS Institute Inc.). Pharmacokinetic analysis will be performed using a non-compartmental analysis (NCA) approach.

The following PK parameters will be calculated for quizartinib and AC886, as applicable.

Cmax	Maximum concentration, determined directly from individual concentration-time data
Tmax	Time of the maximum concentration
Kel	The observed terminal rate constant; estimated by linear regression through at least three data points in the terminal phase of the log concentration-time profile
t1/2	The observed terminal half-life
AUClast	Area under the concentration-time curve from time-zero to the time of the last quantifiable concentration; calculated using the linear trapezoidal rule
AUCinf	Area under the concentration-time curve from time-zero extrapolated to infinity
AUCextr (%)	The percentage of AUCinf based on extrapolation Note: If AUCextr is greater than 20%, AUCinf and related parameters (CL/F and Vz/F) for the specific treatment will be summarized with and without subjects for whom AUCextr >20%.
Clast	The last quantifiable concentration determined directly from individual concentration-time data
Tlast	Time of the last quantifiable concentration
CL/F	Clearance after extravascular administration (for quizartinib only)
Vz/F	Volume of distribution in the terminal phase (for quizartinib only)
MPR AUClast	Metabolite-to-parent ratio for AUClast, AUClast(AC886)/AUClast
MPR AUCinf	Metabolite-to-parent ratio for AUCinf, AUCinf (AC886)/AUCinf

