- c A full physical examination that includes an evaluation of the head, eyes, ears, nose, and throat and the cardiovascular, dermatological, musculoskeletal, respiratory, gastrointestinal, and neurological systems will be performed at Screening, and on Day -1, Day 14, and EOS.
- d BMI at Screening only
- e Female subjects (WOCBP only)
- f Naturally postmenopausal female subjects only
- g Blood samples for hematology and serum chemistry will be collected after a 10-hour fast at Screening, and on Day -1, Day 7, predose (quizartinib) on Day 15, and on Day 19, Day 27, and EOS.
- h Triuplicate ECG (approximately 2 minutes apart) and after at least 5 minutes of quiet rest in the supine position. When a blood collection is scheduled concomitantly with an ECG, the ECG should be taken at least 5 minutes prior to the blood collection and at predose, 2, 4, and 8 hours after quizartinib administration.
- i Vital signs will be taken after at least a 5-minute supine rest; vital signs should be taken at all ECG timepoints.
- j Efavirenz will be dosed as 600 mg once daily from Day 1 through Day 35. Efavirenz will be taken before bedtime on an empty stomach (no food for at least 2 hours before and after dosing).
- k A single dose of 60-mg quizartinib (2 × 30 mg) will be administered following an overnight fast of 10 h on Day 15. Water consumption will be restricted from 1 hour predose to 2 hours postdose, except for the 240 mL of water that is to be administered with quizartinib. Subjects will continue to fast for 4 hours postdose.
- l Day 15 through 36 (relative to quizartinib) PK samples for quizartinib will be collected at predose, 1, 2, 4, 6, 8, 12, 24, 48, 72, 96, 144, 216, 288, 360, 432, and 504 hours post-quizartinib dose. Quizartinib and AC886 showed temperature- and concentration-dependent partitioning into blood cells; therefore, blood samples must be processed at room temperature for determination of plasma quizartinib and AC886 concentrations.

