## 2. INTRODUCTION

### 2.1. Background

Quizartinib is a novel oral Class III receptor tyrosine kinase (RTK) inhibitor exhibiting highly potent and selective but reversible inhibition of Feline McDonough sarcoma (FMS)-like tyrosine kinase 3 (FLT3). At clinically relevant concentrations, quizartinib also binds to KIT proto oncogene receptor tyrosine kinase (KIT) (another RTK), but with lower affinity than to FLT3, and has little or no affinity for other RTKs. Quizartinib has been approved in Japan for the treatment of adult patients with relapsed/refractory FLT3-ITD-positive acute myeloid leukemia (AML). Currently quizartinib is being studied alone or in combination with other agents as a treatment for AML and myelodysplastic syndrome (MDS) in adult and pediatric populations.

Following oral administration, the peak exposure of quizartinib and its major active metabolite, (AC886) occurs at a median of approximately 4 h (range: 2 h to 8 h) and 5 h (range: 4 h to 120 h) postdose, respectively. The plasma exposure of quizartinib and AC886 increased proportional with the dose of quizartinib over a dose range of 20 mg to 90 mg. At steady state, AC886 exposure was approximately 60% of the parent steady state exposure. In vitro reaction phenotyping using human liver microsomes and recombinant human CYP enzymes showed that both quizartinib and AC886 are primarily metabolized by CYP3A and have estimated effective half-lives ( $t_{1/2}$ ) of 73 h and 119 h, respectively. Additionally, AC886 is also formed from quizartinib by CYP3A.

In a previously conducted dedicated hepatic impairment (HI) study in subjects with mild and moderate HI as defined by Child Pugh score, quizartinib exposure increased approximately 30% and 15% increase in AUCinf, respectively. The total active exposure (AUC) of quizartinib plus AC886 increased in subjects with mild HI by 17%, which was not considered clinically meaningful. Quizartinib can be administered with pH modifying drugs such as proton pump inhibitors, H2 antagonists, or antacids, and without regard to food. Strong CYP3A inhibitor (ketoconazole) and moderate CYP3A inhibitor (fluconazole) increased quizartinib AUC by 94% and 20%, respectively. Strong CYP3A inducer rifampin decreased quizartinib AUC by approximately 70%; however, due to bioanalytical issue, the results were not quantitatively conclusive. Therefore, this study aims to evaluate the effect of a moderate CYP3A inducer, efavirenz, on quizartinib PK.

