### **3. OBJECTIVES, OUTCOME MEASURES, AND ENDPOINTS**

#### **3.1. Primary Objective/Endpoint**

The primary objective of this study is:

- To determine the effect of efavirenz on the plasma PK of quizartinib and AC886 in healthy subjects.

The primary endpoints of this study are:

- Plasma PK parameters (Cmax AUClast, AUCinf) for quizartinib and its active metabolite (AC886); additionally Tmax, t1/2, metabolite-to-parent ratio (MPR) AUClast, and MPR AUCinf for quizartinib and its active metabolite (AC886), and CL/F and Vz/F for quizartinib only.

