### **9.2. Sample Size Determination**

The number of subjects planned for this study was not based on statistical power considerations.

With the assumed intersubject coefficient of variation (CV) of 35%, a target sample size of 30 (15/treatment) was calculated to provide 90% confidence that the estimated ratios (with and without efavirenz) of quizartinib geometric mean Cmax and AUC values would be within 20% of true population values. Therefore, 32 subjects (16 subjects in Treatment Group A and 16 subjects in Treatment Group B) will be enrolled in the study to target at least 30 subjects to complete the PK evaluation.

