## **9.5. Statistical Analysis**

The statistical analysis plan (SAP) will be developed and finalized before database lock and will describe the subject populations to be included in the analyses, and procedures for accounting for missing, unused, and spurious data. This section is a summary of the planned statistical analyses of the primary and secondary endpoints.

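### Does the linear trapezoidal rule bias the quizartinib AUC ratios enough to need replacing?

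*Combined protocol and SAP*

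**What the plan says.** Section 9.5.3.1 defines AUClast for quizartinib and AC886 alike as "calculated using the linear trapezoidal rule". AUCinf adds an extrapolated tail, and the two metabolite-to-parent ratios (MPR) divide the AC886 AUC by the quizartinib AUC. Section 3.1 makes these primary endpoints: "Plasma PK parameters (Cmax AUClast, AUCinf) for quizartinib and its active metabolite (AC886"). Section 9.5.3.2 compares the groups by ANOVA on the log scale, with a 90% confidence interval for the ratio A/B.

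Sampling is the same in both groups. In the footnotes to Tables 1.1 and 1.2 the later times are "12, 24, 48, 72, 96, 144, 216, 288, 360, 432, and 504 hours post-quizartinib dose", so the gaps after 12 h are 12, 24, 24, 24 and 48 h, and then 72 h up to 504 h.

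Section 2.1 says that both analytes "are primarily metabolized by CYP3A and have estimated effective half-lives" of 73 h and 119 h. It also reports a fall of about 70% in quizartinib AUC with rifampin, but adds that "due to bioanalytical issue, the results were not quantitatively conclusive".

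Section 9.5.3 says the analysis is "conducted in accordance with the protocol, SAP, and the Daiichi Sankyo Non-Compartmental Analysis Guidelines". Those guidelines are not among the documents. Section 9.5 adds: "The statistical analysis plan (SAP) will be developed and finalized before database lock".

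**The concern.** Between two points on an exponential decline, a straight line lies above the curve. The excess grows with the gap divided by the half-life. From 144 h the 72 h gaps are about one quizartinib half-life in Group B. If efavirenz raises systemic clearance, the same gaps span more half-lives in Group A, so the excess is larger there and does not cancel in the ratio.

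The ratio would then lie too close to 1, and the study would understate the interaction it is meant to measure. The usual alternative, linear while concentrations rise and logarithmic while they fall (log-down), is a standard software setting. It therefore looks as if an avoidable bias has been written into a primary endpoint.

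**Working it through.** **1. The plan's own precision figure.** Section 9.2 reads "With the assumed intersubject coefficient of variation (CV) of 35%, a target sample size of 30 (15/treatment"), to bring the ratio within 20% of truth with 90% confidence.
- SD(log) = sqrt(ln(1 + 0.35²)) = 0.340.
- SE = 0.340 × sqrt(2/15) = 0.124.
- With t(28) = 1.701, the half-width on the log scale is 0.211.
- exp(±0.211) = 0.81 and 1.235, so the interval runs from 19% below to 24% above. The stated sample size is consistent with its target.

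**2. One sampling gap.** For decline at rate k over a gap d, let x = kd. The linear rule overstates the area by (x/2)·coth(x/2) − 1.
- Half-life 73 h, gap 72 h: x = 0.684, excess 3.9%.
- Half-life halved to 36.5 h: x = 1.367, excess 15.1%.

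These late gaps carry little of the total area, so the error in the whole AUC is much smaller.

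**3. The whole profile.** From the documents: the sampling times, Tmax 4 h and half-life 73 h. Assumed: one compartment (ka = 1.22/h then gives that Tmax), the effective half-life used as the terminal one, Kel from the last three points, a quantification limit of 0 to 1% of Group B Cmax, and all induction acting through clearance. The true efavirenz ratio is not given, so a range is shown. The overstatement in Group B is 1.25 to 1.28% (AUCinf).

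| True ratio | Overstatement in A | Error in ratio, linear | Error in ratio, log-down |
|---|---|---|---|
| 0.7 | 1.69 to 1.84% | +0.43 to +0.55% | −0.05% |
| 0.5 | 2.08 to 2.33% | +0.79 to +1.04% | −0.12% |
| 0.3 | 2.65 to 3.08% | +1.35 to +1.78% | −0.28% |

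Check at 0.5 with no quantification limit: 1.0233/1.0128 = 1.0104. AUClast ratios agree within about 0.02 percentage points.

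If induction is split equally between clearance and first pass, the error roughly halves. If it is wholly first-pass, the error is within 0.1%. With a quantification limit of 5% of Cmax the sign is no longer fixed: +0.3 to +0.9% (clearance), −0.5 to +0.1% (split), −0.7 to −0.2% (first pass).

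**4. Effect on the interval.**
- A 1.0% shift is ln(1.010)/0.211 = 5% of the half-width. Coverage is about 89.9%.
- A 1.8% shift is ln(1.018)/0.211 = 8% of the half-width. Coverage is about 89.7%.

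**5. What log-down costs in variance.** In simulation with 15 per arm and 10% or 20% residual error (assumed), the SD of the log AUClast ratio rose by about 1%, for example from 0.109 to 0.110. The added variance is 0.110² − 0.109² = 0.00022. The squared bias under the linear rule, using the largest errors above, is ln(1.0055)² = 0.00003 at ratio 0.7, ln(1.0104)² = 0.00011 at 0.5 and ln(1.0178)² = 0.00031 at 0.3. Log-down therefore lowers mean squared error only near 0.3. The SDs are rounded, so this comparison is approximate, but both quantities are tiny.

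**6. AC886 and the MPR.** Which rule suits AC886 depends on the profile assumed.
- With 0 to 50% formed at first pass and a 119 h half-life, the AUCinf ratio error is −1.12 to +1.03% (linear) and −2.48 to −0.50% (log-down). But these models put the Group B peak at about 134, 109 or 45 h, against a stated median of 5 h.
- With 80% formed at first pass (assumed), Tmax is 5 h. With both clearances induced, the AUCinf errors at ratios 0.7, 0.5 and 0.3 are then +0.23, +0.72 and +1.48% (linear) and −0.25, −0.34 and −0.48% (log-down).
- For AC886 AUClast, log-down is generally the more accurate rule: in the late-peaking models, −0.93 to +0.16% against +0.07 to +1.70%.

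Changing the rule for quizartinib alone would put two rules inside the MPR. With linear for both analytes, the error in the A/B contrast of MPR AUClast is −0.3 to +0.1% when clearance is multiplied by 0.8 to 0.5 (as the true parent ratio), and −0.8 to +0.1% at 0.3. With linear for AC886 and log-down for quizartinib it is +0.2 to +1.2% and +1.3 to +2.2%.

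**The case for a change.** The best case for a change is that the quizartinib bias has a known cause and, under clearance induction with a low quantification limit, a known direction. It understates the effect of interest, and log-down nearly removes it in the one-compartment model. The SAP is still to be finalized, so a change would be cheap. Two-compartment models also give larger errors: about 0.5 to 0.8% at ratio 0.7, 0.8 to 1.5% at 0.5 and 0.7 to 2.5% at 0.3.

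The mechanism and direction stand, and so do the wider ranges. Even 2.5% is small against an interval of −19% to +24%. In the same two-compartment models log-down leaves about −0.8 to +0.5%, so it does not remove the error entirely. The cost is also more than one setting. Changing quizartinib alone worsens the MPR AUClast contrast, while changing both analytes takes a position on AC886 that the documents cannot settle. Listing log-down AUCs for both analytes as a sensitivity result would do no harm, provided each MPR uses one rule throughout, but nothing in the interpretation depends on it.

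**Conclusion.** No change follows, because there is no material gain. The linear rule is stated in advance and applied to both groups and both analytes, in a study that Section 9.1 describes as not testing a hypothesis. Its error in the quizartinib AUC ratios is about 0.4 to 1.0% for true ratios of 0.7 to 0.5, up to 1.8% at 0.3 (2.5% with two compartments), and nil if induction is at first pass. Against the planned precision this would not alter how the interaction is read.

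The figures rest on the effective half-life serving as the terminal one and on simple compartmental models. They also depend on assumed values for the true ratio, the mechanism of induction and the quantification limit, none of which the documents give. The ranges cover these unknowns, and none of the cases examined makes the integration error comparable with the sampling error.

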#### **4.1.2. End-of-Study**

At the defined EOS in both treatment groups (Day 36 for Treatment Group A and Day 22 for Treatment Group B), subjects will have a final PK blood sample taken and safety assessments of AEs, laboratory tests, vital signs, ECGs, and physical examination conducted.

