### 7.2. Withdrawal Procedures

In accordance with the Declaration of Helsinki and other applicable regulations, a subject has the right to withdraw from the study at any time and for any reason without prejudice to his or her future medical care by the study physician or at the study site.

If a subject withdraws from the study, s/he will be required to have ET study procedures performed (refer to Section [4.1.2](#)).

If a subject is withdrawn from the study, the Investigator will complete and report the observations as thoroughly as possible up to the date of withdrawal, including the date of last treatment and the reason for withdrawal.

If the subject is withdrawn due to an AE, the Investigator will follow the subject until the AE has resolved or stabilized.

All subjects who are withdrawn from the study should complete protocol-specified withdrawal procedures.

See SoEs ([Table 1.1](#) and [Table 1.2](#)) for data to be collected at the time of study discontinuation and for any further evaluations that need to be completed.

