#### 9.5.3.2. Statistical Analysis of Pharmacokinetic Endpoints

Plasma concentrations at each nominal timepoint and the PK parameters of quizartinib and AC886 will be summarized by Treatment Group at each nominal timepoint using descriptive

statistics: n, mean, standard deviation (SD), minimum (min), median, maximum (max), and coefficient of variation (CV%), geometric mean, and geometric CV%, as appropriate.

Cmax, AUClast, and AUCinf will be compared between Treatment Group A (quizartinib plus efavirenz; Test) and Treatment Group B (quizartinib alone; Reference). These comparisons between groups will be performed using an ANOVA model and based on logarithm-transformed Cmax, AUClast, and AUCinf. The resulting point estimates (least-squares means) differences between Treatment Group A and Treatment Group B, and 90% CIs for the difference will be exponentiated to get the ratio (Test/Reference) and corresponding 90% CI of the ratio on the untransformed scale.

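### Should the 20% extrapolation note in section 9.5.3.1 also cover the metabolite-to-parent ratios and AUClast?

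*Combined protocol and SAP*

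**What the plan says.** Section 3.1 names Cmax, AUClast and AUCinf as primary endpoints and goes on: "additionally Tmax, t1/2, metabolite-to-parent ratio (MPR) AUClast, and MPR AUCinf for quizartinib and its active metabolite (AC886"). CL/F and Vz/F follow, for quizartinib only.

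Section 9.5.3.1 opens its parameter table with "The following PK parameters will be calculated for quizartinib and AC886, as applicable". It defines AUCextr as the extrapolated percentage of AUCinf, and AUClast as the area up to the last quantifiable concentration. The two ratios are "Metabolite-to-parent ratio for AUCinf, AUCinf (AC886)/AUCinf" and "Metabolite-to-parent ratio for AUClast, AUClast(AC886)/AUClast". The note under AUCextr reads: "AUCinf and related parameters (CL/F and Vz/F) for the specific treatment will be summarized with and without subjects for whom AUCextr >20" per cent.

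Section 9.5.3.2 gives the between-group analysis: "These comparisons between groups will be performed using an ANOVA model and based on logarithm-transformed Cmax, AUClast, and AUCinf". Neither ratio is in that model.

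On early departure, section 7.2 says "If a subject withdraws from the study, s/he will be required to have ET study procedures performed", and section 4.1.2, to which it refers, says "subjects will have a final PK blood sample taken and safety assessments of AEs".

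Section 9.4.1 admits evaluable dosed subjects with enough data for one parameter. Section 9.5 calls itself a summary and leaves missing and spurious data to a SAP to be finalised before database lock. Section 9.5.3 adds the sponsor's non-compartmental guidelines. Neither source is in the documents.

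**The concern.** The parenthesis in the note reads like a closed list. MPR AUCinf is a quotient of two AUCinf values, so it inherits any doubt about either, yet it is not on the list. Because CL/F and Vz/F are calculated for quizartinib alone, the note names no related parameter for AC886, the analyte with the longer half-life. Read literally, a subject flagged on AC886 leaves one of the two AUCinf summaries but stays in the only MPR AUCinf summary, so the ratio cannot be matched to the reduced AUCinf table.

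A second worry is the subject who withdraws after quizartinib. A final sample is taken, AUClast stops there, and a shortened AUClast enters the summary and the ANOVA without a flag, while AUCinf from the same profile is shown both ways. Third, the note speaks of summaries and does not say which AUCinf set enters the ANOVA.

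At stake would be consistent reporting across primary endpoints and, for a very early withdrawal, some bias in the AUClast ratio.

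**Working it through.** **Inputs.** Effective half-lives 73 h (quizartinib) and 119 h (AC886), and median Tmax 4 h and 5 h (AC886 range 4 to 120 h), from section 2.1. Last sample at 504 h, from the schedules of events. Sixteen per group and an intersubject CV of 35%, from section 9.2. Assumptions: one-compartment decay with the effective half-lives used as terminal ones; AC886 either formed fast or, as an upper bound, formed only from a 73 h parent.

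**The plan's own figure.** Section 9.2 gives 15 per group for 90% confidence within 20%. With SD 0.35, a t quantile and limits 0.80 to 1.25 (ln 1.25 = 0.223), the log half-width is 0.226 at 14 per group and 0.217 at 15, so 15 is reproduced. The log-scale SD is sqrt(ln(1 + 0.35²)) = 0.340, and the standard error of a log ratio with 16 per group is 0.340 × sqrt(2/16) = 0.120.

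**Step 1: which parameters contain extrapolation?**

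| Parameter | Extrapolated part | In the note |
|---|---|---|
| AUCinf, CL/F, Vz/F | yes | yes |
| MPR AUCinf | yes, from both analytes | not named |
| AUClast, MPR AUClast | none | not named |

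The trigger is the extrapolated share of AUCinf. It has no bearing on an area that stops at the last measured point. Only MPR AUCinf is a real gap.

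**Step 2: how often would completers trigger the note?** With a single-exponential tail, AUCextr = exp(−ln 2 × 504 / t½).

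- Quizartinib: exp(−ln 2 × 504/73) = 0.8%.
- AC886, fast formation: exp(−ln 2 × 504/119) = 5.3%. Upper-bound model: 12.4%.
- AC886 passes 20% at 504 h only if its half-life exceeds about 217 h (fast formation) or 160 h (upper bound).
- For a log-normal half-life with assumed CV of 20% to 35%, the share above the threshold is 1 − Φ(ln(threshold/119)/σ), with σ = sqrt(ln(1 + CV²)). This gives 0.1% to 3.9% (fast formation), or 0.02 to 0.6 of 16, and 7.0% to 19.4% (upper bound), or 1.1 to 3.1 of 16.

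The upper-bound model puts AC886 Tmax at about 134 h, beyond the reported range and far from the 5 h median, so its figures are a ceiling. These are Group B figures. Induction in Group A should shorten the tails.

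**Step 3: when do the analytes disagree?** AUCextr falls to 20% at about 170 h for quizartinib and about 277 h (fast formation) to 415 h (upper bound) for AC886. A last quantifiable sample between those times flags AC886 only, and there the note is silent on MPR AUCinf.

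**Step 4: what does one shortened profile do to AUClast?** With f the share of the 504 h area captured, one Group B subject of 16 multiplies the ratio by exp(−ln f / 16). For quizartinib at 73 h:

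| Last sample | AUCextr | f | Shift in ratio |
|---|---|---|---|
| 24 h | 80% | 0.199 | +10.6% |
| 48 h | 64% | 0.364 | +6.5% |
| 96 h | 40% | 0.600 | +3.2% |
| 144 h | 26% | 0.750 | +1.8% |
| 216 h | 13% | 0.878 | +0.8% |

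The largest is ln 1.106 = 0.101 on the log scale, below the standard error of 0.120. A Group A withdrawal moves the ratio the other way by a similar or smaller amount. For AC886 the Group B shift is +13.5% at 24 h and +3.3% at 144 h under fast formation, with a ceiling of +30.0% and +7.3%.

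**Step 5: does the one-way ANOVA lose anything?** Section 9.5.3.2 names no covariate. If treatment group is the only factor, the ANOVA ratio equals the ratio of geometric means, and geometric means are among the planned summaries. The AUCinf ratio without flagged subjects can then be read from the tables that the note already requires.

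**The case for a change.** The best case for acting is that the protocol chose to write a rule and its list misses a primary endpoint built from the very quantity it distrusts. Elsewhere in the same section examples are marked as such, so the parenthesis does look complete. The SAP was still to be written, the wording would cost nothing, and in an open-label study it is better to settle such choices before concentrations are seen. Section 9.4.1 sets no completeness rule, so a withdrawal's shortened AUClast does go in, and that subject's MPR AUClast could be 75% (fast formation) to 30% (upper bound) of its full value after a stop at 96 h.

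What stands: MPR AUCinf is not named, the analyte that would trigger it is not stated, and the AUCinf set for the ANOVA is left implicit.

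What does not stand is the claim on AUClast and MPR AUClast. Showing them both ways would be a new missing-data analysis with its own trigger, a stop in sampling before 504 h. Section 9.5 assigns that subject to the SAP. The extrapolation note would not even supply the contrast for the largest shifts: in a simulation with 10% assay error, the terminal slope could not be estimated in 40% of profiles cut at 24 h, so no AUCinf existed to show. Nor are these parameters singled out. Half-life rests on the same terminal slope as AUCinf and is also shown one way.

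**Conclusion.** The concern is right on one detail and no change follows from it. The note omits MPR AUCinf, but the sensible reading is plain: a ratio of two AUCinf values is doubtful when either is. The plan's qualifier on where parameters apply, the SAP and the sponsor's guidelines all leave room to handle it so. For the ANOVA, the text names no exclusion, so every subject in the PK population with an AUCinf enters, and the alternative ratio can be recovered from the planned tables.

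The effect is on the completeness of a descriptive table. MPR AUCinf enters no between-group model, section 9.1 tests no hypothesis, and under fast formation fewer than one of 16 Group B completers would be flagged (ceiling 3.1). One shortened quizartinib profile moves the AUClast ratio by less than one standard error even at 24 h, and by under 2% from 144 h. AC886 could move more after a very early withdrawal, but that is a missing-data question separate from this note.

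These sizes rest on effective half-lives standing in for terminal ones, one-compartment decay, an assumed half-life CV of 20% to 35%, and a single withdrawal. Several early withdrawals in one group would add up, and the SAP's missing-data rules are the place for that.
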